APPENDIX 1 – MEN Count Study Protocol

Background

The Making Employment Needs (MEN) Count intervention was originally developed and pilot tested using a community-based participatory research approach via funding from the National Institute of Mental Health Grant R21MH085614 grant in Boston, MA.¹ The MEN Count study aimed to determine the efficacy of the MEN Count intervention in terms of its impact on incident STI and heterosexual risk for HIV (i.e., unprotected sex with multiple female sex partners in the past 90 days) among Black heterosexual men (n=454). The two armed quasi-experimental evaluation study enrolled participants in either the MEN Count counseling intervention or an attention comparison group focused on stress reduction. Participants were assessed via survey and HIV/STI testing at baseline and 6- and 12-month follow-ups to test the hypotheses that MEN Count participants, relative to attention comparison participants, would: (a) report a reduction in sexual risk, as measured by unprotected sex episodes and transactional sex in the past 90 days at each follow-up; and (b) have lower incident STI across the follow-up period. This study also aimed to examine the MEN Count intervention's impact on social determinants of health outcomes including employment and homelessness, as well as the intervention's impact on expected mediators (i.e. masculinity ideologies, social-structural factors, and social-cognitive factors) of behavior change, and to explore whether these factors mediated the relationship between the intervention and study outcomes.

Methods/Design

Setting

This study primarily took place in a local STI clinic in Washington D.C.

Curriculum Development

After pilot testing, prompts were embedded into the curriculum to identify checkpoints when MEN Count case managers (CMs) should provide referrals for HIV/STI testing. Prompts were also added to help CMs inquire about the participant's employment situation, potential violence in relationships, HIV/STI testing history and managing HIV risk.

MEN Count Peer Counselors

MEN Count CMs received professional development and training opportunities related to: stress management, anger management, DC resource referrals, mental health status assessment, substance abuse or addiction detection, sensitivity training about gender and sexual identity and LGBT diversity, healthy masculinity, and case note writing.

Pilot Testing

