Each session included: 1) Personalized employment, housing stability and sexual risk assessments; 2) Guided examination of why identified risks (e.g., multiple sex partners, non-condom use) occur, considering theory-supported risk factors including traditional masculinity ideologies, substance use, mental health, and low HIV/STI knowledge and risk perceptions; 3) Identification of social or health service (e.g., substance abuse treatment and mental health services) referrals or known job opportunities to reduce concurrent sexual partnerships affected by these concerns; 4) Support for maintenance in stable job or housing situations when frustrations about these occur; and 5) Problem solving via an action plan of concrete steps the client could take to reduce non-condom sex practices and to stabilize their housing and employment; and recognition/positive reinforcement of enactment of action plans (Sessions 2&3).

Figure 1: Structure and Timing of MEN Count Intervention Delivery over 60-90 Days

"Washington D.C., 2014-2017"

Attention-Comparison Condition. The stress education and reduction program offered to control condition participants followed the same 60-90 day 3-session structure of the MEN Count intervention. This program focused on how to reduce stress and tension via diet, exercise, and effective

communication. Excluded from focus were issues of HIV/STIs, substance use, and masculinity ideologies. The program did retain linkage to job placement and housing resource provision, however.

Eligibility

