At recruitment, staff screened potential study participants to assess eligibility. Eligible participants self-identified as Black or African American men, aged 18 years or older and English fluent; reported sex with two or more women in the past 12 months AND unprotected vaginal sex in the past 12 months; reported homelessness in the past 6 months (at least one night in shelter or on the streets) OR current unemployment (currently having no legal employment for money); were willing to participate in the MEN Count program, complete surveys, and be tested for STIs; and could provide contact information for themselves and two other individuals through whom we could reach them. Exclusion criteria were outlined on the basis of their potential impact on study participation or intervention testing effects. Participants were excluded from the study if they: planned to leave Washington D.C., Maryland, or Virginia in the next 6 months, were cognitively impaired (based on Folstein Mini-Mental Exam at recruitment or baseline testing), and/or had self-reported health status that prohibited them from participating in the program.

Methods for Data Collection.

Quantitative. Study staff used mobile tablet surveys to collect detailed data on participants' demographics, risk behaviors, HIV/STI risk profile, and HIV/STI knowledge, attitudes and risk perceptions. Trained research staff conducted surveys in a private room at the study site. Study participants could opt to enter their survey responses directly into the tablet survey system in real-time on their own, or study staff could enter responses. Study staff uploaded completed surveys securely and directly to a secure server system. For STI testing, researchers collaborated with a D.C. area STI clinic and established a confidentiality agreement to share participant HIV/STI test results for only those participants that enrolled in the study and consented to have their HIV/STI results shared for the purposes of this study. The STI clinic shared participant HIV/STI test results with the program manager securely on a monthly basis. In order to link baseline survey and follow-up data, surveyors uploaded research ID-assigned (i.e., de-identified) test result data to the database.

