Power calculations were conducted based on an intended sample size of 504 and assumed two-sided tests with a 0.05 type I error rate. Power calculations were focused on reduction of STI incidence as it was the more conservative analysis. A 25% attrition rate, assumed to be high and to be expected for this population, resulted in an assumed $n=378$ participants at follow-up. Power calculations were based on a two-sided Poisson regression of a dependent variable of counts (i.e. number of incident STI cases) on a binary independent variable (treatment group) with proportion of 0.50 (i.e. 189 participants) in each group adjusting for age, marital status, employment and homelessness (assuming the estimated R-squared of the independent variable regressed on these four covariates is 0.04). The estimates used for these power calculations were based on a recent HIV intervention study with young Black heterosexual men recruited from STI clinics. The STI clinic study found that comparison group participants were almost 3 times as likely to be STI-infected at follow-up relative to intervention participants. MEN Count pilot data were too small to see intervention impact on STI but did document a baseline STI rate of 13% in this target population. Using these data, the proposed sample size of $n=378$ would have at least 80% power to detect a rate ratio (Group 1/Group 2) of at least 0.28 (intervention incidence rate=2%), 0.31 (intervention incidence rate=2.5%), 0.34 (intervention incidence rate=3%) or 0.36 (intervention incidence rate=3.6%), respectively, assuming the 1-year cumulative STI incidence rate in the Comparison Group is 7%, 8%, 9%, or 10%.

Though difference-in-difference multivariate regression models were used to assess outcomes (see below), analyses were also performed as outlined by power calculation assumptions (e.g. utilizing Poisson models and specified covariates) and also found null results for the incident STI outcome.

Analytic Plan

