Outcome analyses were designed to focus on four outcomes of interest (defined in greater detail below): incident non-viral STI, sexual risk, homelessness, and unemployment. The primary comparison of outcomes by treatment group was assessed using mixed-effects multivariate regression models (logistic and multinomial, dependent on outcome) with random effects on individual to account for repeated measurements over time. The treatment effect was evaluated via a time-by-treatment arm interaction term. A categorical time effect was used. This treatment effect can be interpreted as the individual-level effect of the intervention, and this analytic strategy addresses problems of attrition, missing data, variable timing of subject visits and other possible unintended violations of design common to longitudinal studies. Demographic covariates were included in all outcome models if they were significantly associated with treatment group at baseline in bivariate chi-squared tests at $p<0.20$. For each outcome, additional potential covariates were included if they were associated with the given outcome in bivariate chi-squared tests at $p<0.05$. Dose effects of the MEN Count intervention were evaluated using a similar analytic strategy, examining a time-by-dose interaction instead of time-by-study arm.

Outcome Definitions

Pursuant to previous HIV prevention research with Black heterosexual men that used ordinal index of sexual risk categorization, sexual risk was categorized as very low, low, medium, and high.² Very low sexual risk was defined as having one partner and consistent condom use. Low sexual risk was defined as having multiple partners and consistent condom use OR one partner and no/inconsistent condom use. Medium sexual risk was defined as having multiple partners, no/inconsistent condom use and not participating in transactional sex. High risk was defined as having multiple partners, no/inconsistent condom use, and participating in transactional sex. Participants reporting sex with men in the prior 90 days (n=20) or who reported that they themselves or (one of) their partner(s) was HIV-positive (n=31) were excluded from the sexual risk outcome analysis given the known differential HIV risk profile for these subpopulations and small numbers of participants in each.

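### Hypothesis (a) is about unprotected sex episodes, but the plan never analyses their number: condom use enters only as all-or-none within a four-level index

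*Combined protocol and SAP*

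**What the plan says.** All references are to the Combined protocol and SAP.

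- **Background.** Under hypothesis (a), intervention participants would "report a reduction in sexual risk, as measured by unprotected sex episodes and transactional sex in the past 90 days at each follow-up". The same section words the study aim differently, as "unprotected sex with multiple female sex partners in the past 90 days".
- **Intervention.** Sessions worked on both condom use and partner numbers: "concrete steps the client could take to reduce non-condom sex practices" and "known job opportunities to reduce concurrent sexual partnerships affected by these concerns".
- **Eligibility.** Men had to have "reported sex with two or more women in the past 12 months AND unprotected vaginal sex in the past 12 months". This look-back is 12 months; the outcome look-back is 90 days.
- **Analytic Plan.** Four outcomes are listed, and sexual risk is the only behavioural risk outcome among them. The models are "mixed-effects multivariate regression models (logistic and multinomial, dependent on outcome"). No count model is described for sexual behaviour.
- **Outcome Definitions.** "sexual risk was categorized as very low, low, medium, and high". The levels combine partner number, condom consistency and transactional sex. A man is a consistent user only if his protected acts equal his total acts. Transactional sex is defined as a component of the index and separates only the top two levels.

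**The concern.** The hypothesis names a frequency, and the analysis keeps only whether that frequency is zero. Counselling that leads men to use condoms more often, but not always, is a plausible result of sessions aimed at condom use. The planned outcome gives no credit for it.

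The documents report no sexual-risk result, so the question is how one should be read. If the index showed no difference between arms, a reader could take hypothesis (a) as refuted although one of its two stated measures had never been examined as stated. The tablet survey already collected total and condom-protected acts, so the information exists.

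**Working it through.** **Step 1. What the index can register.** The definitions cross partners (0, 1, 2+), consistent condom use (yes, no) and transactional sex (yes, no): 3 × 2 × 2 = 12 combinations.

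| Partners | Consistent | No transactional sex | Transactional sex |
|---|---|---|---|
| 0 | either | no level | no level |
| 1 | yes | very low | very low |
| 1 | no | low | low |
| 2+ | yes | low | low |
| 2+ | no | medium | high |

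Eight combinations have exactly one level. The four with no partner have none. For a man with no acts the condom ratio is 0/0, while the equality rule would call him consistent; he still fits no level, because very low requires one partner.

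A man who goes from 40 unprotected acts to 1, with partners and transactional sex unchanged, keeps his level.

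**Step 2. Inputs for an illustration.** The plan gives no figure on this point to reproduce. From the Power Calculation: 504 × 0.75 = 378, and 378 / 2 = 189 per arm. Everything else is assumed: unprotected acts negative binomial with mean 10 or 20 and size k from 0.2 to 1; 70% of men with multiple partners and 30% with transactional sex, independent of acts; one visit, no covariates, no reporting error. This is not an estimate for the planned three-wave model.

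**Step 3. Why the mechanism decides.** The share with zero unprotected acts is P0 = (k / (k + mean))^k. With k = 1:
- Mean 10: 1/11 = 0.091.
- Every man's acts halved, mean 5: 1/6 = 0.167, a rise of 7.6 points. Across the settings the rise is 4 to 8 points.
- Instead, 30% of men become fully consistent: 0.091 + 0.30 × 0.909 = 0.364, a rise of 27 points, although the mean falls by only 30%.

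The count test is z = ln(ratio of means) / SE, with SE² = [(1/m1 + 1/k) + (1/m2 + 1/k)] / 189 under the negative binomial.
- k = 0.2, mean 10 to 5: SE = √[(5.1 + 5.2)/189] = 0.233; z = 0.693/0.233 = 2.97; power = Φ(2.97 − 1.96) = 0.84.
- k = 1: SE = √[(1.1 + 1.2)/189] = 0.110; z = 6.3; power = 1.00.

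**Step 4. Simulated power, two-sided 0.05.** Count: robust Wald test on the log ratio of means. Index: 3-df likelihood-ratio test of the 2 × 4 table.

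| Assumed change in the intervention arm | Count | Index |
|---|---|---|
| Every man's acts halved | 0.85-1.00 | 0.10-0.19 |
| 30% of men become fully consistent | 0.30-0.83 | 0.55-0.99 |
| 30% of multi-partner men move to one partner | about 0.05 | 0.70-0.94 |
| No effect | 0.04-0.06 | 0.04-0.07 |

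A repeat with 1,500 trials per setting agreed with these ranges to within simulation error. If every man's acts fall by 30%, the count test has 0.36-0.93 and the index 0.04-0.12, so the count can itself be weak.

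**Step 5. Transactional sex.** Assume prevalence falls from 30% to 20%. Direct test: z = 0.10 / √[(0.21 + 0.16)/189] = 2.26, so power = Φ(2.26 − 1.96) = 0.62, or Φ(2.26 − 2.24) = 0.51 at alpha 0.025. Suppose that 50%, 65% or 80% of the men concerned have multiple partners and less than fully consistent condom use, and that medium plus high holds 50% of all men. The high-versus-medium contrast then has simulated power of about 0.35, 0.48 and 0.61.

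**The case against.** The strongest reply is that a composite may properly stand for sexual risk. This one has a cited precedent in the same population and contains both elements of hypothesis (a). Medium plus high together match the aim as the Background words it. It also registers fully consistent condom use and fewer partners, both of which fit the session content. All of that stands. It is why the index should stay, and why the first row of the power table must not be read alone: the second and third rows reverse the ranking.

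A second reply concerns transactional sex. A reader might infer that the plan loses this measure altogether. It does not. Transactional sex changes the level only among men with multiple partners and less than fully consistent condom use, but eligibility selects towards such men, and the multinomial model can isolate the step. A separate model tested at 0.025 (0.51) would be about level with the contrast at a 65% share (0.48) and behind it at 80% (0.61). What remains is that no reference level or contrast is named.

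A third reply concerns the exclusions from the index: men reporting sex with men (n=20) and those with HIV in themselves or a partner (n=31). Hypothesis (a) does not mention them, but the aim is heterosexual risk and the plan gives its reason. They are not a defect.

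Finally, the study is over and the Power Calculation section says that the analyses "also found null results for the incident STI outcome". Any added model is therefore post hoc. That limits what it can claim, but it does not make the count uninformative.

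**Conclusion.** The concern holds for the number of unprotected episodes. The plan describes no analysis of it, and the all-or-none rule makes the index blind to any reduction short of zero. This follows from the definitions and depends on no assumed figure. A null index result would leave that part of hypothesis (a) unanswered.

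The size of the loss depends on how behaviour changed, which the documents do not say. If all men cut back in proportion, it is large. If some men switched to full condom use or to one partner, the index is the better measure. The power figures rest on the assumed act counts, dispersion and cell shares, so they show direction and range only.

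Two stronger readings are not supported. One is that the index is invalid or generally insensitive; the reversed rankings rule that out. The other is that men with no partner in the past 90 days were dropped and the comparison biased. Their handling is unstated, but nothing shows that they were omitted or that their numbers differ by arm. That point calls for clarification only.

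**What to change.** 1. Keep the four-level index and its mixed multinomial model as they are. Name the reference level and report the high-versus-medium contrast.
2. Add one analysis: number of unprotected acts (total minus condom-protected) in a mixed negative binomial model with the planned categorical time-by-arm term. Use participant-level robust or bootstrap standard errors. In simulations with no effect, model-based errors rejected 0.09-0.18 of the time when acts were in fact Poisson-lognormal.
3. Run it in the index analysis set, with all participants who have the items as a sensitivity analysis. Label it post hoc and report the estimate with a confidence interval.
4. A mixed logistic model of any transactional sex is optional. If it is added, apply Holm across the two models.
5. As a clarification, state how men with no partner in the past 90 days were classified, with counts by arm and visit. Beside the existing result, show the index with these men in the very-low level as a labelled sensitivity analysis.

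The cost is a re-analysis of existing survey items and a few lines of text, with no new data. The drawback is one or two further post hoc models, which inform hypothesis (a) but cannot confirm it.
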